9.5. Analysis methods - primary outcome(s)

A template for reporting the primary outcome is given in Appendix D6.

The primary outcome is a composite measure of episode mortality or failure to clear lactate and is measured as a binary outcome. Participants clearing less than 20% per hour of their lactate between randomisation and 2 hours after randomisation or dying between time of injury/recruitment and discharge to non-acute care will be defined as experiencing the primary outcome. The primary outcome measure will be summarised as the number of participants experiencing the primary outcome with percentages.

Adjusted relative risks (adjusted for IDS) along with 95% confidence intervals will be estimated using a log-binomial regression model. Statistical significance of the treatment group parameter

will be determined from the p-value generated by the model. The absolute risk difference along with 95% confidence intervals will be estimated using a binomial regression model with identity link. As this is a composite endpoint, the primary outcome will also be reported in accordance with the recommendations of Ferreira-Gonzalez et al¹¹, with the qualifying event for the primary outcome presented using the template in Appendix D6a.

See section 9.1 for details on covariate adjustment and model convergence.

9.6. Analysis methods - secondary outcomes

A template for reporting the secondary outcomes is given in Appendix D7.

Binary outcomes (e.g. development of ARDS, mortality at pre-specified time-points) will be analysed in the same way as the primary outcome.

Continuous outcomes (e.g. pre-hospital fluid volume, vital signs, OFFS) will be summarised using means and standard deviations, or medians and IQRs if appropriate. Adjusted mean differences (adjusted for IDS and baseline values) along with 95% confidence intervals will be estimated using a linear regression model. Statistical significance of the treatment group parameter will be determined from the p-value generated by the model.

9.7. Analysis methods - exploratory outcomes and analyses

Bayesian analysis of the primary composite outcome measure, and each component separately, will be performed as exploratory analyses to quantify the probability of treatment effects of different sizes. The PHBP and Crystalloid intervention arms will be modelled separately, with the outcome assumed to be a random deviate from a Bernoulli distribution. Priors will take the form of independent beta(a, b) distributions and are set to model the probability of a participant achieving the primary outcome in each arm. Three sets of priors are specified: non-informative priors, skeptical priors such that the probability of observing a treatment effect at least as large as the specified relative risk ratio of 0.82 is less than 5%, and informative priors reflecting current knowledge. For each set of the priors, the table below provides the values of the shape parameters used to specify the beta distributions, summary statistics (mean, variance, median, upper and lower 2.5% quantiles), and simulated probabilities of exceeding three different treatment effect sizes (expressed as relative risk ratios).

	Priors					
	Non-informative		Skeptical		Informative	
	Crystalloid	PHBP	Crystalloid	PHBP	Crystalloid	PHBP
a	1	1	50	50	7	3
b	1	1	25	25	3	2
Mean	0.5	0.5	0.667	0.667	0.7	0.6

Variance	0.0833	0.0833	0.003	0.003	0.019	0.04
2.5%	0.025	0.025	0.557	0.557	0.400	0.194
Median	0.5	0.5	0.668	0.668	0.714	0.614
97.5%	0.975	0.975	0.768	0.768	0.925	0.932
Pr(RR \leq 0.82)	0.410		0.0442		0.444	
Pr(RR \leq 0.70)	0.350		0.0015		0.313	
Pr(RR \geq 1.54)	0.325		0.0002		0.054	

For example, the informative prior for the PHBP group is set as beta(3,2), reflecting the assumption that the primary outcome rate in the PHBP group is unlikely to be lower than 19% or greater than 93%. For the Crystalloid group, the informative prior is set as beta(7,3), reflecting the assumption that the primary outcome rate in the Crystalloid group is unlikely to be lower than 40% or greater than 93%. Relative risk ratios of 1.54³ and 0.70⁴ were reported in two recent pre-hospital RCTs using plasma in one of the treatment arms. The informative priors are specified such that the probabilities of observing treatment effects less than or equal to 0.70 and greater than or equal to 1.54 are 31.3% and 5.4% respectively. Under the sceptical priors these probabilities are 0.15% and 0.02% respectively.

Adjusted relative risks (adjusted for IDS), along with 95% highest density intervals (HDIs) will be estimated using a Bayesian log-binomial regression model. The posterior probabilities that the relative risk ratio was less than 1, 0.8, and 0.7 will be calculated. Similarly, risk differences, adjusted for IDS, along with 95% HDIs will be estimated using a Bayesian binomial regression model with an identity link. The posterior probabilities that the risk difference was less than 0%, 10%, and 20% will be calculated. A template for reporting is given in Appendices D10 to D10b.

9.8. Safety data

The number and percentage of participants experiencing any adverse events, serious adverse events (SAEs) and suspected unexpected serious adverse reactions (SUSARs) will be presented by intervention group. Statistical significance will be determined by a chi-squared test. The total number of SAEs in each group will also be given along with a descriptive table of the details of the events. A template for reporting this data is given in Appendix D8.

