5.1. Confidence intervals and p-values

All estimates of differences between groups will be presented with two-sided 95% confidence intervals, unless otherwise stated. P-values will be reported from two-sided tests at the 5% significance level.

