5.2. Adjustments for multiplicity

No correction for multiple testing will be made

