9.1. Covariate adjustment

In the first instance, intervention effects between groups for all outcomes will be adjusted for IDS (stratification variable; see section 4.6) as a fixed effect (this will be the primary analysis). A secondary analysis adjusting for IDS and the following prognostic variables (age, lactate, cardiac arrest and Glasgow Comma Score (GCS) at randomisation) as fixed effects will also be undertaken for the primary outcome measure (and the individual components).

For binary outcomes, if the log-binomial model fails to converge, a Poisson regression model with robust standard errors will be used to estimate the same parameters.⁹ If this also fails to converge, unadjusted estimates will be produced from the log-binomial model. It will be made clear in the final report why this occurred (e.g. not possible due to low event rate/lack of model convergence).

Longitudinal secondary outcomes (e.g. vital signs, venous lactate concentration, etc.) will also be adjusted for their baseline values.

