Appendix D8: Safety

	PHBP (N=)	Crystalloid (N=)	p-value
Transfusion-related lung injury	n (%)	n (%)	p-value
Any thromboembolism	n (%)	n (%)	p-value
Deep-vein thrombosis	n (%)	n (%)	p-value
Pulmonary embolism	n (%)	n (%)	p-value
Stroke	n (%)	n (%)	p-value
Other	n (%)	n (%)	p-value
Infection (suspicion, or clinical evidence of)	n (%)	n (%)	p-value
Intra-abdominal	n (%)	n (%)	p-value
Meningitis	n (%)	n (%)	p-value
Respiratory	n (%)	n (%)	p-value
UTI	n (%)	n (%)	p-value
Soft tissue	n (%)	n (%)	p-value
Indwelling device	n (%)	n (%)	p-value
Blood-born	n (%)	n (%)	p-value
Other	n (%)	n (%)	p-value

	PHBP (N=)	Crystalloid (N=)	p-value
Total number of SAEs	n	n	
Total number of participants experiencing an SAE	n (%)	n (%)	<insert p-value>
Total number of SUSARs	n	N	
Total number of participants experiencing an SUSAR	n (%)	n (%)	<insert p-value>

A line by line listing of each SAE may be appropriate for some studies and can be included in an Appendix to the main report; the table below provides a guide for how the line listing of SAE data could be presented.

Summary of SAE	Reason for Reporting	Causality	Action taken
PHBP			
1 <insert description of			

SAE>			
2			
3			
4			
Crystalloid			
1			
2			
3			
4			

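### Section 9.8 tests every Appendix D8 safety row by chi-squared with no small-count rule and no effect estimate, so the p-value of an individual sparse row can mislead

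*SAP*

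**What the plan says.** Section 9.8 sets out what is counted in each arm, namely those "experiencing any adverse events, serious adverse events (SAEs) and suspected unexpected serious adverse reactions (SUSARs) will be presented by intervention group". For the comparison between arms it adds: "Statistical significance will be determined by a chi-squared test". It mentions no exact alternative, continuity correction or threshold for small counts. It then refers to the layout: "A template for reporting this data is given in Appendix D8".

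Appendix D8 has a p-value column for 15 event rows, among them "Transfusion-related lung injury", stroke, pulmonary embolism and meningitis. It has two further p-values, for participants with an SAE and for "Total number of participants experiencing an SUSAR". That makes 17 tests. The columns are the two arms and the p-value; there is no effect estimate or confidence interval.

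Three general rules bear on these tests:

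- Section 5.1: "P-values will be reported from two-sided tests at the 5% significance level".
- Section 5.2: "No correction for multiple testing will be made".
- Section 9.1: "intervention effects between groups for all outcomes will be adjusted for IDS", where IDS is the intervention delivery site. Section 5.3 counts safety among the outcomes.

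The convergence fallback in 9.1 applies to regression models, not to this test. Fisher's exact test is named only in the sample-size section (4.7).

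**The concern.** The chi-squared p-value relies on a large-sample approximation, which is usually not trusted when an expected cell count is below 5. Several D8 rows name events that could plausibly occur only a few times in a trial of this size. In such a row a small one-sided cluster of events could be reported as a statistically significant harm or benefit of blood products when an exact test would not call it so. Because D8 shows nothing but counts and a p-value, no interval would tell the reader how little information the row carries.

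The unadjusted test also departs from the promise in 9.1 to adjust all outcomes for site, and the SAP does not say that safety is an exception. If the statistician changed to an exact test after seeing sparse tables, that would be a deviation to be explained in the Appendix A table.

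**Working it through.** **Denominators.** Section 9.8 gives no figures, so the arm sizes come from section 4.7: 219 per group, and 490 in total after allowing for 10% loss. The 219 reproduces. For 20% against 10%, two-sided 5% and 80% power:

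- n = [1.96·√(2·0.15·0.85) + 0.8416·√(0.2·0.8 + 0.1·0.9)]² / 0.1² = 199 per group.
- With continuity correction: (199/4)·[1 + √(1 + 4/(199·0.1))]² = 219.
- Exact Fisher power at 219 per arm is 0.812.
- 438/0.9 = 487, against 490 stated.

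Analysis by intention to treat with 1:1 allocation gives up to 490/2 = 245 per arm, so I used 220 to 245.

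**When is a row sparse?** With equal arms and t events in total, the smallest expected count is t/2. It is below 5 when t < 10, that is, when the pooled event rate is under 10/490 = 2.0%. The SAP gives no rates, so whether a given row falls here is an assumption.

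**P-values.** With equal arms, N in total, t events and a difference of d events between arms, the uncorrected statistic is N·d²/[t·(N − t)].

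- 4 vs 0 at N = 490: 490·16/(4·486) = 4.03, p = 0.0446.
- Fisher for the same table: 2·(245·244·243·242)/(490·489·488·487) = 0.1235.

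| Split (245 per arm) | Smallest expected count | Chi-squared, uncorrected | Chi-squared, Yates | Fisher |
|---|---|---|---|---|
| 3 vs 0 | 1.5 | 0.082 | 0.247 | 0.249 |
| 4 vs 0 | 2.0 | 0.045 | 0.132 | 0.123 |
| 5 vs 0 | 2.5 | 0.025 | 0.072 | 0.061 |
| 6 vs 0 | 3.0 | 0.014 | 0.040 | 0.030 |
| 6 vs 1 | 3.5 | 0.057 | 0.128 | 0.122 |
| 7 vs 1 | 4.0 | 0.032 | 0.075 | 0.068 |
| 8 vs 1 | 4.5 | 0.019 | 0.044 | 0.037 |

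Results at 219 and 220 per arm agree to within 0.001. For fewer than 10 events and equal arms, the two tests fall on opposite sides of 0.05 for three splits only: 4 vs 0, 5 vs 0 and 7 vs 1.

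**Dependence on equal arms.** For 4 vs 0, with n₁ the size of the arm that has the events and n₂ the other, the statistic is 4·N·n₂/[n₁·(N − 4)]. At N = 490 it exceeds the critical value 3.84 only if n₂/n₁ > 3.84/4.03 = 0.953, so significance is lost once the arm with the events is about 5% larger than the other.

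**Error rate averaged over event totals.** Exact enumeration of two equal binomial arms of 245:

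| True event rate in both arms | Chi-squared, uncorrected | Fisher |
|---|---|---|
| 0.5% | 2.1% | 0.1% |
| 1% | 4.5% | 0.8% |
| 2% | 4.6% | 2.0% |
| 3% | 5.1% | 2.5% |

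**Error rate given the event total.** At 220 per arm the chance that uncorrected chi-squared gives p < 0.05 under no effect is 0% for 2 or 3 events, then 12.3%, 6.1%, 3.0%, 1.5%, 6.8% and 3.7% for totals of 4 to 9. It swings around 5% instead of sitting above it.

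**The case against.** The strongest defence is that the planned test keeps its nominal error rate. Averaged over event totals, uncorrected chi-squared is at or very near 5% or below, while Fisher is far below it at low rates. In safety work, where missing a harm is the greater worry, preferring the less conservative test is a recognised choice. This stands. A reader might infer from the 4 vs 0 example that the plan inflates false safety signals overall; the enumeration does not support that.

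Three further limits also stand:

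- The SAP does not say which chi-squared statistic is meant. With Yates correction 4 vs 0 gives 0.132, and the discrepancy with Fisher disappears in all three splits.
- The exact answer depends on the version used. Mid-p at 220 per arm gives 0.062 for 4 vs 0, but 0.031 for 5 vs 0 and 0.038 for 7 vs 1, so those two stay below 0.05. A plan that left Fisher and mid-p open would not settle them.
- Not all safety questions run through this test. ARDS and transfusion-related complications, the subject of secondary objective VII, are secondary outcomes under 9.6 and Appendix D7, with a site-adjusted relative risk and 95% confidence interval.

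What the defence does not answer is that a p-value in a single row is read as evidence about that row, and that D8 offers nothing to read beside it.

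**Conclusion.** The point holds as a minor gap in 9.8 and D8. Where a row has fewer than 10 events, the planned p-value can fall below 0.05 when Fisher's does not: 0.045 against 0.123 for 4 vs 0, and 0.025 against 0.061 for 5 vs 0. This rests on three assumptions: that some D8 rows are that sparse, that the uncorrected statistic is used, and that the arms are nearly equal in size. The first cannot be checked from the SAP. One might conclude from the kinds of event listed that most rows will be sparse, but the SAP contains no rates to support that.

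The missing interval and the unstated exception to 9.1 do not depend on these assumptions. The primary and secondary analyses are untouched.

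**What to change.** Change 9.8 and D8 as follows:

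1. Use Fisher's exact test, two-sided, for any row with an expected count below 5, and chi-squared otherwise. Name one exact version; do not leave a choice with mid-p. State whether the chi-squared statistic is continuity-corrected.
2. Add to every D8 row that carries a p-value a risk difference with an exact 95% confidence interval, name the interval method, and make this the main comparative measure.
3. State in 9.8 that safety comparisons are not adjusted for IDS, as an exception to 9.1.

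This costs a few sentences and an extra column in the template, with no new data. The statistical cost is that Fisher is conservative: its error rate is about 0.1% to 2.5% for event rates of 0.5% to 3%, so a real harm in a sparse row is less likely to reach p < 0.05. The interval should therefore be read alongside the p-value, and a non-significant sparse row should not be reported as evidence of no difference.

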9.9. Planned subgroup analyses

Interpretation of subgroup analysis will be treated with caution (output will be treated as exploratory rather than definitive¹²). Analysis will be limited to the primary outcome of a composite measure consisting of episode mortality and lactate clearance only, and the following subgroups:

- IDS
- Mode of PHEM transport (air vs ground)
- Initial lactate concentration (≤ 2.2 mmol/L vs >2.2 mmol/L)

- Time to ED from injury (≤1 hour vs >1 hour)
- Mode of injury (blunt vs penetrating vs crush)
- Volume of pre-hospital fluid given (total intervention (4 boluses) vs <4 boluses)
- Age (<50 years, 50-70 years, >70 years)
- Head injury (positive vs negative)
- Compressible haemorrhage (compressible haemorrhage vs non-compressible haemorrhage)
- Pre-morbid drug history (anticoagulant or antiplatelet medication vs no anticoagulant or antiplatelet medication)
- Age of blood products (<8 days vs ≥8 days)
- Cardiac arrest (arrested vs not arrested)

The effects of these subgroups will be examined by including a treatment group by subgroup interaction parameter in the regression model. A template for reporting the subgroups analyses for the primary outcome is given in Appendix D9.

The anticipated magnitude and direction of differential treatment effects in each of the subgroup analyses are:

- IDS: regional differences in PHEM protocols and system characteristics may alter the effect of the intervention. However, the anticipated direction of effect is unclear in the subgroup analysis for IDS and this analysis will be regarded as purely exploratory.
- Mode of PHEM transport (air vs ground): ground transport typically takes longer than air transport, thus a greater effect of intervention may be observed in those being transported by ground.
- Initial lactate concentration (≤2.2 mmol/L vs >2.2 mmol/L): participants with an abnormal initial lactate concentration (>2.2 mmol/L) may have a higher incidence of the primary outcome event and may exhibit a greater benefit from PHBP.
- Time to ED from injury (≤1 hour vs >1 hour): participants taking >1 hour to arrive in ED from injury take longer to receive definitive treatment. Thus, a greater effect of intervention may be observed in participants taking more than >1 hour to arrive and receive definitive treatment in ED.
- Mode of injury (blunt vs penetrating vs crush): the anticipated direction of effect is unclear in the subgroup analyses for mode of injury and this analysis will be regarded as purely exploratory.
- Volume of pre-hospital fluid given (total intervention (4 boluses) vs <4 boluses): the volume given is considered a surrogate for the volume of blood loss. Participants receiving <4 boluses of pre-hospital fluid may have experienced less blood loss and a lower incidence of the primary outcome event. Thus, they may exhibit a reduced effect from PHBP.
- Age (<50 years, 50-70 years, >70 years): mortality is greater in the more elderly groups. Therefore, the intervention is anticipated to have a greater effect in the >70 years cohort.

- Head injury (positive vs negative): Major haemorrhage increases the risk of secondary brain injury We anticipate that the intervention effect may be greater in those with head injury
- Compressible haemorrhage (compressible haemorrhage vs non-compressible haemorrhage): the anticipated direction of effect is unclear in the subgroup analyses for compressible haemorrhage and this analysis will be regarded as purely exploratory
- Pre-morbid drug history (anticoagulant or antiplatelet medication vs no anticoagulant or antiplatelet medication): the degree of haemorrhage will be greater in those with anticoagulation medication Therefore, we anticipate that the intervention may have a greater effect in those participants on anticoagulant medication
- Age of blood products (<8 days vs ≥8 days): fresh blood has better oxygen carrying capacity than old blood, therefore we anticipate that the intervention may have a greater effect in those participants receiving fresher blood (<8 days old)
- Cardiac Arrest: participants experiencing a cardiac arrest may have a higher incidence of the primary outcome event, but may be less likely to demonstrate any differential treatment effect due to the severity of their condition

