Appendix D10b: Exploratory Bayesian analysis for lactate clearance	43

1. Introduction

This document is the Statistical Analysis Plan (SAP) for the RePHILL trial, and should be read in conjunction with the current trial protocol. This SAP details the proposed analyses and presentation of the data for the main paper(s) reporting the results for the RePHILL trial.

The results reported in these papers will follow the strategy set out here. Subsequent analyses of a more exploratory nature will not be bound by this strategy, though they are expected to follow the broad principles laid down here. The principles are not intended to curtail exploratory analysis (e.g. to decide cut-points for categorisation of continuous variables), nor to prohibit accepted practices (e.g. transformation of data prior to analysis), but they are intended to establish rules that will be followed, as closely as possible, when analysing and reporting data.

Any deviations from this SAP will be described and justified in the final report or publication of the trial (using a table as shown in Appendix A). The analysis will be carried out by an appropriately qualified statistician, who should ensure integrity of the data during their data cleaning processes.

2. Background and rationale

The background and rationale for the trial are outlined in detail in the protocol. In brief, the administration of high ratios of plasma to packed red blood cells (PRBC) has been widely adopted for in-hospital treatment of major traumatic haemorrhage. Acceptance of in-hospital haemostatic resuscitation saw the British military implement it for battlefield casualty retrieval. With the increasing adoption of giving Pre-Hospital Blood Products (PHBP) for trauma in both the UK and abroad, in both military and civilian settings, it is important to determine whether this intervention is effective. The provision of PHBP requires considerable logistical and financial resources and RePHILL will establish a high quality evidence base for PHBP resuscitation.

3. Trial objectives

The primary objective is to investigate the clinical effectiveness of PHBP resuscitation compared to the current standard care of restricted crystalloid based resuscitation in participants suffering from major traumatic haemorrhage.

Secondary objectives are to test the hypotheses that, when compared to standard care, does PHBP resuscitation:

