- I. Improve blood pressure, heart rate and capillary oxygenation on Emergency Department (ED) arrival?
- II. Prolong on-scene time?
- III. Reduce pre-hospital fluid requirements?
- IV. Reduce in-hospital transfusion requirements?

- V. Reduce trauma-induced coagulopathy?
- VI. Preserve platelet function?
- VII. Lead to a greater incidence of transfusion-related complications, particularly acute respiratory distress syndrome (ARDS)?
- VIII. Lead to blood product wastage?
- IX. Affect haemoglobin concentration levels on ED arrival?

4. Trial methods

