4.6. Randomisation

Participants will be randomised at the level of the individual in a 1:1 ratio to either PHBP (Lyophilised Plasma LyoPlas N-w (LyoPlas) and PRBC) resuscitation or crystalloid (0.9% sodium chloride [normal saline]) resuscitation.

Randomisation will be performed centrally at the Birmingham Clinical Trials Unit (BCTU) using stratification by intervention delivery site (IDS) to account for variation in trauma care and type of trauma between delivery sites.

In the RePHILL trial, the blood banks will maintain a constant supply of randomised trial interventions to the Pre-Hospital Emergency Medical (PHEM) team. The blood bank will obtain the randomised allocations via a secure online system at the BCTU.

Blood banks will be supplied with pre-printed 'treatment box number' labels. A registered user at the blood bank will request a treatment allocation from the BCTU and will receive a treatment box number and treatment arm allocation. The allocated trial intervention will be packed into transport boxes affixing the correct labels. Transport boxes will be issued as a pair, one marked red and one marked yellow per single randomised allocation. The packed, sealed transport

boxes will be dispatched to the PHEM base using an established courier service as required

On-scene, the PHEM doctor will assess the potential participant's vital signs on scene and confirm if eligible for entry into the RePHILL trial. If they fulfil the eligibility criteria for the trial, the randomised treatment will be given. Participants are considered randomised into the trial when the PHEM team open the first transport box containing the allocated trial intervention.

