Appendix B: Trial schema

PHEM doctor assesses patient at the trauma scene and confirms eligibility (see protocol section 4) for randomisation into the RePHILL Trial

Capillary lactate concentration measured immediately prior to intervention using a point of care device

PHEM doctor opens sealed transport boxes

Randomised Intervention

Fluid boluses will be given to restore a palpable radial pulse or a measured standard SBP above 90 mmHg

Crystalloid-based resuscitation arm:

Up to 4 boluses of 250 ml Sodium Chloride 0.9% (normal saline)
2 x 250 ml bags per box

Pre-hospital blood product resuscitation arm: Up to 4 units of PHBP given as follows:

1 unit PRBC → 1 unit LyoPlas
1 unit PRBC → 1 unit LyoPlas

Arrive at receiving hospital

Refer to protocol section 7

- Vital signs
- Standard coagulation and FBC
- Lactate clearance
- ROTEM[®] (designated sites)
- Platelet function (designated sites)

Informed consent for continued participation in the trial

Hospital admission

Inpatients will be followed-up for up to 30 days[†]

Presence/absence of ARDS

Organ dysfunction

Adverse event monitoring

[figure not shown]
Survival[‡]

Data cleaning & analysis

[figure not shown]
[†] For some mortality data will be collected up to discharge from the acute care setting which may be >30 days

[figure not shown]

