Appendix D2a: Prehospital timeline by group

The duration in minutes between the time of the 999 call and prehospital events. Values above the diagonal correspond to the PHBP group and values below the diagonal correspond to the Crystalloid group.

Prehospital event	999 Call	On-scene attendance	Randomisation Capillary Lactate	Treatment box opening	Left Scene*	Arrival at ED**
999 call		Median (IQR) (n N)	Median (IQR) (n N)	Median (IQR) (n N)	Median (IQR)	Median (IQR)

					(n N)	(n N)
On-scene attendance	Median (IQR) (n N)		Median (IQR) (n N)	Median (IQR) (n N)	Median (IQR) (n N)	Median (IQR) (n N)
Randomisation Capillary Lactate	Median (IQR) (n N)	Median (IQR) (n N)		Median (IQR) (n N)	Median (IQR) (n N)	Median (IQR) (n N)
Treatment box opening	Median (IQR) (n N)	Median (IQR) (n N)	Median (IQR) (n N)		Median (IQR) (n N)	Median (IQR) (n N)
Left Scene*	Median (IQR) (n N)	Median (IQR) (n N)	Median (IQR) (n N)	Median (IQR) (n N)		Median (IQR) (n N)
Arrival at ED**	Median (IQR) (n N)	Median (IQR) (n N)	Median (IQR) (n N)	Median (IQR) (n N)	Median (IQR) (n N)	

*Added in v4.0 of pre-hospital CRF (active in all sites from 29th August 2019)

**These numbers are lower than the totals of randomised participants due to deaths on-scene or during transit to hospital.

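### Fluid volume (wholly) and time to ED (partly) arise after randomisation, so their treatment-by-subgroup interactions are open to bias

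*SAP*

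**What the plan says.** Section 9.9 lists "Volume of pre-hospital fluid given (total intervention (4 boluses) vs <4 boluses" and "Time to ED from injury (≤1 hour vs >1 hour" among the subgroups for the primary outcome. On method it says: "The effects of these subgroups will be examined by including a treatment group by subgroup interaction parameter in the regression model". Appendix D9 gives both the same rows as age or initial lactate: a relative risk per level and an interaction p-value. Section 9.9 also states a direction for each. It expects less effect with fewer than 4 boluses, because volume is taken to stand for blood loss, and more effect when the journey exceeds 1 hour.

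Section 4.6 fixes the moment of randomisation: "Participants are considered randomised into the trial when the PHEM team open the first transport box containing the allocated trial intervention". Section 3 introduces its list with "Secondary objectives are to test the hypotheses that, when compared to standard care, does PHBP resuscitation"; item III is "Reduce pre-hospital fluid requirements" and item II asks about longer on-scene time. Section 4.4 makes pre-hospital time and fluid type and volume secondary outcomes, and Appendix D7 compares them between arms.

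**The concern.** An interaction test asks whether the treatment effect differs between kinds of patient. The randomised comparison carries over within a subgroup when membership is settled before treatment can act on it. If treatment can move people across the cut, the two arms within a stratum hold different mixes of patients, and the stratum relative risk combines the treatment effect with that difference in mix.

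Section 9.9 treats bolus count as a patient characteristic, while sections 3 and 4.4 treat fluid volume as something PHBP may change. At stake are two rows of D9 with pre-stated directions. A pattern produced by the sorting alone could be read as confirming the plan's hypothesis, or as benefit or harm confined to one group.

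**Working it through.** **What sets the bolus count.** Four influences can be read from the SAP.
- Response to the allocated fluid. Appendix B: "Fluid boluses will be given to restore a palpable radial pulse or a measured standard SBP above 90 mmHg". The trial is open-label (section 4.1).
- Transport time. Section 5.4 accepts arrival at ED before the second bolus as a reason for not giving it.
- Early death. A participant who dies after one bolus is in the <4 stratum, which section 9.9 expects to have fewer events, yet that death is itself an event.
- The arm. In Appendix B, four boluses are 4 × 250 ml saline in one arm and 2 PRBC plus 2 LyoPlas in the other, so the label is not one exposure.

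**What sets time to ED.** The interval from injury to box opening precedes randomisation; the rest follows it. Treatment matters only for those it moves across 1 hour. Participants who die before arrival have no ED time. The footnote to the arrival column in D2a says "These numbers are lower than the totals of randomised participants due to deaths on-scene or during transit to hospital". All these deaths are primary-outcome events (section 9.4), and section 9.9 does not say how they are classified. If they were left out, and 5% to 10% of participants died before ED (assumption), the share of events lost at the 65% pooled rate in section 4.7 would be 5/65 = 8% to 10/65 = 15%.

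**Plan figures.** The SAP gives no figure for these subgroups. From section 4.7, 490 × 0.9 = 441, about 220 evaluable per arm. Exact Fisher power at 220 per arm for 71.7% vs 58.3% is 81.8%, against the stated 80%, so the design figures are a sound base.

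**Simple illustration, no true effect (65% in both arms).** Assume half of controls receive 4 boluses (risk 75%) and half fewer (55%). PHBP moves some participants, whose risk is 65%, from 4 to <4.
- 20% moved: risk with 4 is (0.375 − 0.130)/0.30 = 0.817, RR 0.817/0.75 = 1.09; risk with <4 is (0.275 + 0.130)/0.70 = 0.579, RR 0.579/0.55 = 1.05. Ratio of RRs 1.035.
- 10% moved: 0.310/0.40 = 0.775, RR 1.03; 0.340/0.60 = 0.567, RR 1.03. Ratio 1.003.

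The overall RR is 1.00 in both cases. The interaction test at 220 per arm rejects 5.7% and 5.0%. This shows distorted subgroup RRs and almost no distortion of the interaction.

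**Model with graded severity.** Let severity U be standard normal. Control risk is Φ(a + bU) with mean 71.7%; PHBP risk is RR times that, so there is no true interaction. The chance of 4 boluses is Φ(c + dU), with c set in each arm to give the assumed share; b and d are 1 or 2. Risk in a stratum is E[p·v]/E[v], where p is the event risk and v the chance of being in that stratum. Results for true RR 0.82, with ranges over b and d:

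| Share with 4 boluses, control → PHBP | RR, 4 boluses | RR, <4 | Ratio of RRs | False rejection |
|---|---|---|---|---|
| 40% → 40% | 0.82 | 0.82 | 1.000 | 5.0% |
| 40% → 30% | 0.83–0.84 | 0.86–0.90 | 0.98–0.92 | 5.3–9.5% |
| 40% → 20% | 0.84–0.86 | 0.90–0.97 | 0.96–0.87 | 5.9–20% |
| 60% → 40% | 0.86–0.87 | 0.92–1.10 | 0.94–0.79 | 7.2–29% |

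With true RR 1.00 and the same shifts, the apparent RR is 1.02 to 1.06 with 4 boluses and 1.05 to 1.34 with fewer; false rejection is 5.5% to 35%. In this model the artefact shows less benefit with <4 boluses, the direction section 9.9 anticipates. In the simple illustration the ratio lies slightly the other way, so the direction depends on who is moved.

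**The case against.** A reader might infer that the plan expects treatment to change both variables, and that both interactions are therefore biased. The SAP does not support that. Section 3 poses questions to be tested. The time question concerns on-scene time, which is one part of the interval from injury to ED, and much of that interval precedes randomisation. Bias needs a shift, and the SAP reports none. The mildest cases above leave the test close to 5%, and no interaction bias has been calculated for time to ED.

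Section 9.9 makes all subgroup output exploratory, to be read with caution, and confines it to the primary outcome. D4, D7 and D2a show units given, fluid volume and timings by arm, so readers could see whether a shift occurred. The omission of pre-ED deaths is an inference from a footnote about the timeline table; section 9.9 itself is silent.

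These points stand and limit the claim to possible bias. They do not make the two analyses valid. An exploratory label tempers interpretation but does not restore comparability within strata, and nothing in 9.9 or D9 marks these rows as different in kind from age or initial lactate.

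**Conclusion.** The concern holds as a risk of bias. For fluid volume the case is strong: the variable is wholly post-randomisation, titrated to response, affected by transport time and early death, and a different exposure in each arm. For time to ED it is weaker: the variable is only partly post-randomisation, and the added fault is that participants who die before arrival have no stated place in the subgroup.

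Under the assumed shifts, false rejection of the fluid interaction runs from about 5% to 29% (true RR 0.82) or 35% (true RR 1.00). The bolus shares, severity slopes and pre-ED death rate are all assumptions; with no shift in the model there is no bias. The primary analysis and the sample size are untouched. This is a worthwhile correction to an exploratory section.

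**What to change.** Remove fluid volume and time to ED from the interaction analyses in section 9.9 and from D9. Alternatively, keep them as descriptive tables labelled post-randomisation, without relative risks or interaction p-values; for time to ED, show deaths before arrival as their own category.

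If a severity or delay subgroup is wanted, use baseline variables already collected, such as on-scene systolic pressure (Appendix D2) and time from 999 call to box opening (D2a), with cut-points set before the analysis.

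The cost is wording in section 9.9 and D9, with no new data. Two planned rows are lost, and the replacements are related to the originals without being equivalent: delay to box opening is not delay to definitive care, and on-scene pressure is not blood loss.
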